*Characterisation of users for the assessment of risk minimisation measures (SmPC changes):* Users of cilostazol will be characterised to evaluate the impact of the risk minimisation measures that Otsuka submitted to the EMA in October 2012. For this evaluation, DUS2 is planned to be initiated 6 months after the implementation of the SmPC changes, and results will be compared with those obtained in DUS1. Evaluation of the impact of the risk minimisation measures will be conducted through the following variables according to the sections of the SmPC:

- **Indications:** Smoking status at the start date; number of patients with a visit to the general practitioner and/or to a specialist between 3 months and 4 months after the start date; number of patients discontinuing cilostazol between 3 months and 4 months after the start date
- **New contraindications:** Number of patients with a recorded diagnosis for unstable angina pectoris, myocardial infarction, or coronary intervention, within 6 months before the start date; number of patients with concurrent use of two or more platelet aggregation inhibitors at the start date and during follow-up

- Warnings and precautions: Patients with a history of arrhythmias, hypotension, or coronary heart disease recorded at any time before the start date will be followed to assess the rates of visits to general practitioners or specialists
- Posology: Reduction of daily dose to 100 mg will be assessed among patients who are prescribed a potentially interacting medication or a potent inhibitor of CYP3A4 or CYP2C19 during current use of cilostazol.

Use of cilostazol will be evaluated for the use in patients with diseases and conditions currently listed as contraindications in the SmPC that will be retained in the revised SmPC. These conditions are severe renal impairment, moderate to severe hepatic impairment, congestive heart failure, history of bleeding disorders, and history of arrhythmias.

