### 9.3.4 Concurrent Use of Medications That May Interact With Cilostazol

Cilostazol is extensively metabolised by cytochrome P-450 (CYP450) enzymes, particularly CYP3A4 and to a lesser extent by CYP2C19. Medications potentially interacting with cilostazol are listed in the risk management plan and in the summary of product characteristics and include CYP3A4 and CYP2C19 substrates and inhibitors and CYP3A4 inducers. A summary of these medications is presented in Table 6. A complete list of clinically relevant medications interacting with CYP450 is presented in Annex 3.

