**Table 6. Medications Potentially Interacting With Cilostazol**

Medication	Substrates		Inhibitors		Inducers
	CYP2C19	CYP3A4	CYP2C19	CYP3A4	CYP3A4
Proton pump inhibitors					
Lansoprazole	X		X		
Omeprazole	X		X		
Antiepileptics					
Phenytoin	X				X
Carbamazepine					X
Macrolide antibiotics					
Clarithromycin		X		X	
Erythromycin		X		X	
Protease inhibitor antivirals					
Indinavir		X		X	
Ritonavir		X		X	
Nelfinavir				X	
Gastrointestinal					
Cisapride		X			
Calcium channel blockers					
Diltiazem		X		X	
Statins					
Simvastatin		X			
Antimycotics					
Ketoconazole			X	X	
Itraconazole				X	
Antimycobacterials					
Rifampin					X

Medication	Substrates		Inhibitors		Inducers
	CYP2C19	CYP3A4	CYP2C19	CYP3A4	CYP3A4
Antipsychotics					
Pimozide		X			

CYP = cytochrome P-450.

For each user of cilostazol, the use of each medication listed in Annex 3 will be ascertained at the start date and during follow-up for current use of cilostazol (Section 9.3.1).

- Concurrent use at the start date:
  - Patients who have at least one prescription for a potentially interacting medication recorded within 3 months before the start date
- Concurrent use during follow-up:
  - Patients who have at least one prescription for a potentially interacting medication recorded during the time of current use of cilostazol.
  - Patients who have at least one prescription for a potentially interacting medication recorded during the time of consecutive use of cilostazol as defined in Section 9.3.1 (duration of use of cilostazol).

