#### 9.3.4.1 Concurrent Use of Potent Inhibitors of CYP3A4 and CYP2C19

Concurrent use of potent inhibitors of CYP3A4 and CYP2C19 will also be evaluated. Potent inhibitors are those identified as such by the Indiana Classification (Trustees of Indiana University, 2013) and the United States Food and Drug Administration Drug Development and Drug Interactions website. Potent inhibitors are lansoprazole, fluvoxamine, nefazodone, ticlopidine, clarithromycin, troleandomycin, indinavir, ritonavir, nelfinavir, mibefradil, ketoconazole, and itraconazole.

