### **9.3.6 Baseline Characterisation of New Users for the Assessment of Planned Risk Minimisation Measures (SmPC Changes)**

New users of cilostazol will be characterised to evaluate the impact of the risk minimisation measures that Otsuka submitted to the EMA in October 2012. The risk minimisation measures include SmPC changes to identify a more restricted target population and to decrease the daily dose when cilostazol is used with potentially interacting medications. The risk minimisation measures also include communication initiatives to HCPs.

To evaluate the impact of the risk minimisation measures, a second DUS (DUS2) will be initiated 6 months after the implementation of the SmPC changes, and results will be compared with those obtained in the first DUS (DUS1).

The SmPC changes and the characteristics of users that will be evaluated in DUS1 and DUS2 are detailed in Table 7.

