**Table 7. Proposed Changes in the Labelling of Cilostazol and Characterisation of Users**

Proposed Change to Summary of Product Characteristics	Characterisation in DUS
Restricted target population	
Indication	
4.1 Cilostazol is for second-line use in patients in whom life-style modifications (including smoking cessation and [supervised] exercise programmes) and other appropriate interventions have failed to sufficiently improve their intermittent claudication symptoms	Smoking status a
4.2 The physician should reassess the patient after 3 months of treatment with a view to discontinuing cilostazol where an inadequate effect is observed.	Number of patients seen by the treating physician after 3 months b Number of patients discontinuing after 3 months b
Contraindications	
4.3 Patients with unstable angina pectoris, myocardial infarction within the last 6 months, or a coronary intervention in the last 6 months	Unstable angina Myocardial infarction Coronary intervention
Patients treated concomitantly with two or more additional antiplatelet agents (e.g., aspirin, clopidogrel)	Concurrent use of two or more platelet-aggregation inhibitors
Other SmPC changes	
Warnings and precautions	
4.4 Based on its mechanism of action, cilostazol may induce tachycardia, palpitation, tachyarrhythmia, and/or hypotension. The increase in heart rate associated with cilostazol is approximately 5 to 7 beats per minute; in patients at risk, this may induce angina pectoris.	
Patients who may be at increased risk for serious cardiac adverse events as a result of increased heart rate, e.g., patients with stable coronary disease or a history of tachyarrhythmias, should be monitored closely during the treatment with cilostazol; the use of cilostazol in patients with unstable coronary disease or coronary intervention within the last 6 months is contraindicated (see SmPC Section 4.3).	Number of visits to general practitioner and/or specialist

Proposed Change to Summary of Product Characteristics	Characterisation in DUS
Posology	
4.2 Reduction of the dose to 50 mg twice daily is recommended in patients receiving medicines that strongly inhibit CYP3A4, e.g., several macrolides, azole antifungals, protease inhibitors, or medicines that strongly inhibit CYP2C19, e.g., omeprazole.	Daily dose

CYP = cytochrome P-450; DUS = drug utilisation study; SmPC = Summary of Product Characteristics.

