  - Patients with a history of arrhythmias, hypotension, or coronary heart disease recorded at any time before the start date will be followed to assess the rates of visits to general practitioners or specialists. Visit rates for these patients will be used as a proxy of intensified monitoring and compared with the rates for the patients who do not have a history of arrhythmias, hypotension, or coronary heart disease.
- Posology
  - Daily dose of cilostazol at the start date will be assessed among concurrent users of potentially interacting medications at the start date
  - Reduction of daily dose to 50 mg will be assessed among patients who are prescribed a potentially interacting medication during continuous use of cilostazol.

The diagnosis, procedure, and medication codes that will be used to define the variables for the evaluation of the risk minimisation measures are included in Table 4 and Table 5.

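### No starting-dose result is specified for strong CYP3A4/CYP2C19 inhibitor users, the group named in Table 7; the only potent-inhibitor dose result counts 200-to-100 mg reductions, on a list without omeprazole

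*Protocol*

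**What the plan says.** **The label change.** The posology row of Table 7 reads "Reduction of the dose to 50 mg twice daily is recommended in patients receiving medicines that strongly inhibit CYP3A4" and extends the advice to "medicines that strongly inhibit CYP2C19, e.g., omeprazole". The characterisation listed against it is daily dose.

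**Starting dose.** The introduction to Section 9.3.6 describes the aim of the measure in wider terms: "to decrease the daily dose when cilostazol is used with potentially interacting medications". Its posology variables then begin: "Daily dose of cilostazol at the start date will be assessed among concurrent users of potentially interacting medications at the start date". Section 9.3.4 says that these medications "include CYP3A4 and CYP2C19 substrates and inhibitors and CYP3A4 inducers", with the full list in Annex 3. Use at the start date means "Patients who have at least one prescription for a potentially interacting medication recorded within 3 months before the start date". In Section 9.7.1, Analysis Table 5 describes starting dose by sex and age group only.

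**Dose reduction.** The abstract says: "Reduction of daily dose to 100 mg will be assessed among patients who are prescribed a potentially interacting medication or a potent inhibitor". Section 9.7.5 specifies a reduction from 200 mg to 100 mg during continuous use, in users of interacting medications (Analysis Table 18A) and in users of potent inhibitors (Analysis Table 18B).

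**The potent list.** Section 9.3.4.1 states: "Potent inhibitors are lansoprazole, fluvoxamine, nefazodone, ticlopidine, clarithromycin, troleandomycin, indinavir, ritonavir, nelfinavir, mibefradil, ketoconazole, and itraconazole". Section 9.7.3 repeats the list, but to count concurrent use, not dose.

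**The concern.** Section 8 says that DUS2 is to evaluate the effect of the SmPC changes on prescribing. The cohort consists of new users. For a new user already taking a strong inhibitor, following the Table 7 text means a first prescription at 100 mg/day. That is the most direct sign that the posology advice was taken up, and it is known on the first day of follow-up. A later reduction needs follow-up time, and in DUS2 follow-up stops on 31 December 2014 (Section 9.2.6), so patients who start late in the year have little of it.

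As specified, the direct sign is visible only in a group mixed with users of substrates and inducers. The one result restricted to potent inhibitors measures something else, and it leaves out the only CYP2C19 drug that Table 7 names. DUS2 could therefore show little change where prescribers had in fact followed the advice, or fail to show that they had not.

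**Working it through.** The protocol states no figure on this point, so the check compares its sections, counts the drug lists and looks at how Table 18B behaves.

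**1. Target group against measured group**

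| Item | Group | Dose outcome |
|---|---|---|
| Table 7, posology | strong CYP3A4 or CYP2C19 inhibitors, e.g. omeprazole | 50 mg twice daily = 100 mg/day |
| Section 9.3.6, starting dose | substrates, inhibitors and inducers | daily dose at start |
| Analysis Table 5 | all users, by sex and age | daily dose at start |
| Analysis Table 18A | potentially interacting medications | 200 to 100 mg |
| Analysis Table 18B | 12 potent inhibitors, no omeprazole | 200 to 100 mg |

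No row combines the Table 7 group with starting dose.

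**2. Count of Annex 3**

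- Drugs listed: 67.
- With an inhibitor mark: 19. Of these, 12 are on the potent list (12/67 = 18% of all drugs) and 7 are not: omeprazole, fluoxetine, erythromycin, amiodarone, cimetidine, diltiazem and verapamil.
- With no inhibitor mark: 67 − 19 = 48 (48/67 = 72%). Of these, 7 are marked as CYP3A4 inducers (phenytoin, phenobarbital, carbamazepine, pioglitazone, troglitazone, rifabutin, rifampin), and 48 − 7 = 41 are marked as substrates only.
- All 12 potent inhibitors are in Annex 3, so their users are inside the wider starting-dose group. Omeprazole is in Annex 3, so its users are in that group and in Table 18A, but not in Table 18B.

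**3. What Table 18B can show**

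Among strong-inhibitor users, let s be the share started on 100 mg/day and r the share of 200 mg starters later reduced to 100 mg.

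- Share reaching the recommended dose: s + (1 − s)r, which rises with s whenever r < 1.
- Table 18B with 200 mg patients as denominator: r, which does not depend on s.
- Table 18B with 100 mg starters also in the denominator: (1 − s)r, which falls as s rises.

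Section 9.7.5 does not say which denominator applies. Under neither does the result rise when starting doses improve.

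**4. Dilution, for illustration only**

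The protocol gives no co-medication prevalence, so these inputs are assumptions. Suppose the share started on 100 mg/day rises from 20% to 60% among strong-inhibitor users and stays at 20% in the rest of the wider group. If strong-inhibitor users are a share w of that group, a pooled figure moves from 20% to 0.60w + 0.20(1 − w):

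- w = 10%: 0.06 + 0.18 = 24%
- w = 20%: 0.12 + 0.16 = 28%
- w = 40%: 0.24 + 0.12 = 36%

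A rise of 40 percentage points in the target group would then appear as a rise of 4, 8 or 16 points.

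**The case against.** The strongest reply is that this is detail for table shells. Sections 4 and 9.7 place the shells in separate files that are not shown, and these may split starting dose further. Section 9.3.6 does not say that the wider group will be reported as one pooled figure, use of each Annex 3 drug is recorded at the start date, and the potent-inhibitor users are a subset of the group named. Both variables needed are already planned, and only the cross-tabulation is missing. This weakens any claim that the information is lost, and none is made. It does not remove the mismatch, because the protocol text itself fixes the starting-dose population, the Table 18B outcome and the drug list, and these do not line up with its own Table 7.

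On omeprazole, the 12-drug list follows a stated rule citing two external classifications, and Table 7 gives the proposed wording, not the approved label. That stands: the discrepancy is shown against Table 7 only, and whether omeprazole qualifies under the cited sources cannot be checked from the protocol. It is a reason to keep the sourced list and add a version with omeprazole, not to replace the list.

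It is also fair to say that a reduction measure is not meant to capture starting dose, that dosage patterns are a secondary objective of a descriptive study, and that the Table 18B denominator alone would be ordinary analysis-plan detail. None of this supplies the missing starting-dose result.

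**Conclusion.** The concern holds. Followed as written, the protocol specifies no dose result that isolates whether new users already on a strong CYP3A4 or CYP2C19 inhibitor were started on 100 mg/day. Those patients are diluted in a wider group, not absent from the study. The potent-inhibitor result in Table 18B cannot register a correct start and excludes the CYP2C19 example in Table 7.

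The size in patients is unknown: the 72% describes drug names, and the 4 to 16 point illustration rests on assumed inputs. The conclusion takes Table 7 as the statement of the label change and the protocol text as the specification, since neither the approved wording nor the table shells are at hand. The change should be made, because it bears directly on the stated purpose of DUS2 and uses data already planned. Confidence is medium.

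**What to change.** In Sections 9.3.6 and 9.7.5:

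- Add the number and percentage of users on 100 mg/day at the start date among users of potent CYP3A4 or CYP2C19 inhibitors at that date, using the window in Section 9.3.4 (a prescription within the preceding 3 months).
- Report that result and Table 18B in two versions: the 12-drug list of Section 9.3.4.1 as it stands, and the same list with omeprazole added (13 drugs).
- State that the Table 18B denominator is patients on 200 mg/day.
- Keep the wider starting-dose result and Table 18A as planned.
- Apply the same grouping to DUS1 and DUS2 so that the comparison is like for like.

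The cost is a few sentences and a re-tabulation of planned dose and co-medication data. DUS1 needs some rework at the database centres, and Section 6.1 already describes it as complete in four databases by 30 January 2015. Denominators in the strong-inhibitor group will be smaller, so the counts should be shown beside the percentages. In IACS, GePaRD and Sweden, Table 9 lists formulation strength instead of prescribed dose, so daily dose must be estimated there. That limit applies equally to the dose results already planned.

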### **9.3 Variables**

#### **9.3.1 Use of Cilostazol and Patterns of Use**

The number of new users of cilostazol and the number of prescriptions, packages, and defined daily dose (DDD) will be ascertained overall and by strength, quantity, and year.

Current use of cilostazol will be ascertained according to the days of supply of each prescription for cilostazol. Days of supply of a prescription are defined as the number of days of intended duration of treatment for that prescription. If days of supply of prescriptions are not recorded in some databases, they will be estimated from descriptive analysis of the number of days between consecutive prescriptions.

Current use is defined as the time involving the days of supply of each prescription plus 7 days to allow for a potential delay in the start of treatment.

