## **Germany**

The German Pharmacoepidemiological Research Database (GePaRD) is a population-based database obtained from statutory health insurance agencies (SHIs) in Germany (Jobski et al., 2012; Kraut et al., 2010; Pigeot and Ahrens, 2008). Ninety percent of the population in Germany is insured with the SHIs. The database covers over 15 million SHI members from all regions of Germany, approximately 17% of the German population (population data from Eurostat, 2012). Membership in SHIs is fairly stable over time. The GePaRD includes the following types of data from all patients enrolled in one of the SHIs: demographics, hospital diagnoses, ambulatory care diagnoses and procedures (coded in the International Statistical Classification of Diseases and Related Health Problems, 10th Revision, German Modification [ICD-10-GM]), and ambulatory prescriptions including date of prescription and date of pharmacy dispensing. Although information on dose is not available, the number of boxes prescribed is recorded for each medication.

The German version of the ICD-10-CM is used for coding diagnoses, and OPS (Operationen- und Prozedurenschlüssel) codes are used for surgical and diagnostic procedures. Types of treatments and diagnostic procedures with exact date are registered according to EBM (Einheitlicher Bewertungsmaßstab) codes, developed for payment of physicians for the outpatient treatment of German SHI patients.

Studies are conducted in collaboration with the Bremen Institute for Prevention Research and Social Medicine (BIPS), University of Bremen, Germany; SHI and health ministry approval is needed for the study.

A total of four SHIs contribute data to the GePaRD. Two of these SHIs, involving approximately 4,000 users of cilostazol, approved participation in the study. Data from a third SHI, which also approved participation and included 44 users of cilostazol, are considered inadequate as follow-up is truncated at the end of 2007. These data will not be included in the study. The fourth SHI denied participation in the study. This SHI denied approval because the study protocol did not include an evaluation of current treatment recommendations from the Federal Joint Committee (G-BA) concerning

cilostazol. Submission of a revised protocol that included additional analyses to evaluate these recommendations was unsuccessful.

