### **9.7.5 Assessment of Changes to the Summary of Product Characteristics**

Analysis Tables 17, 18, and 26: The number and percentage of users by sex and age group (< 70 years, ≥ 70 years) will be calculated for the following conditions:

- Smoking: current, past, non-smoker (Analysis Table 17A)
- Number and percentage of users with at least one visit for any reason with a general practitioner or specialist between (a) 2 months and 4 months after the start date and (b) 1 month and 6 months after the start date, evaluated by the clinical review of a sample of patient profiles (Analysis Table 17B) and by diagnosis codes in all users (Analysis Table 17C). Analysis is restricted to patients who are current users of cilostazol at 3 months after the start date.
- Number and percentage of users with at least one visit for intermittent claudication with a general practitioner or specialist between (a) 2 months and 4 months after the start date and (b) 1 month and 6 months after the start date, evaluated by the clinical review of a sample of patient profiles (Analysis Table 17B) and by diagnosis codes in all users (Analysis Table 17C). Analysis is restricted to patients who are current users of cilostazol at 3 months after the start date.
- Discontinuation of cilostazol between 3 months and 4 months after the start date, evaluated using Kaplan-Meier survival curves (Analysis Table 17A and 26)

- Diagnosis within 6 months before the start date: unstable angina, myocardial infarction, or coronary intervention (Analysis Table 17A)
- Concurrent use of cilostazol and two or more platelet aggregation inhibitors (Analysis Table 17A)
- Reduction of daily dose of cilostazol from 200 mg to 100 mg among concurrent users of cilostazol and (a) potentially interacting medications (Analysis Table 18A) or (b) potent inhibitors of CYP3A4 or CYP2C19 (Analysis Table 18B) during continuous use of cilostazol

Analysis Table 19: Rates of visits to general practitioners and/or specialists among users at increased risk of serious cardiac events (patients with history of arrhythmias, coronary heart disease, or hypotension). Rates of visits per 100 person-years and 95% confidence intervals (CI) will be calculated for these patients and for those who are not considered at increased risk of serious cardiac events. Rate ratios and 95% CIs will be estimated comparing the rates in patients with increased risk with rates in patients without increased risk.

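### The dose-reduction measure has conflicting daily-dose targets (50 mg in Section 9.3.6, 100 mg in the Abstract and 9.7.5), and the derived dose is open to misclassification where it rests on refill intervals

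*Protocol*

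**What the plan says.** The protocol describes the dose-reduction measure in three places and the label change behind it in a fourth.

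- Section 9.3.6, Posology: "Reduction of daily dose to 50 mg will be assessed among patients who are prescribed a potentially interacting medication during continuous use of cilostazol".
- Abstract, Variables: "Reduction of daily dose to 100 mg will be assessed among patients who are prescribed a potentially interacting medication". The sentence goes on to add potent CYP3A4 or CYP2C19 inhibitors.
- Section 9.7.5, for Analysis Tables 18A and 18B: "Reduction of daily dose of cilostazol from 200 mg to 100 mg among concurrent users of cilostazol" who also take an interacting medication or a potent inhibitor.
- Table 7, the label text under evaluation: "Reduction of the dose to 50 mg twice daily is recommended in patients receiving medicines that strongly inhibit CYP3A4", or strongly inhibit CYP2C19.

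Daily dose is calculated from strength, quantity and days of supply (Sections 9.3.1 and 9.7.1). Where days of supply are not recorded, Section 9.3.1 says that "they will be estimated from descriptive analysis of the number of days between consecutive prescriptions". Table 9 lists a prescribed dose for SIDIAP and THIN, but only the formulation strength for IACS, GePaRD and Sweden. Section 9.4.2 says of GePaRD: "Although information on dose is not available, the number of boxes prescribed is recorded for each medication". The same section lists dosage among the Swedish prescription data, which does not match Table 9.

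**The concern.** Dose adaptation with interacting medication is one of the label changes whose uptake DUS2 is meant to evaluate, by comparison with DUS1. Section 9.3.6 defines the variable and Section 9.7.5 defines the table that reports it. If they name different daily doses, two data centres could each follow the protocol and score different events. The DUS1 to DUS2 comparison would then mix definitions.

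The second concern is what the derived dose measures. If the divisor is a refill interval, the result reflects when patients collect their next pack as well as what was prescribed.

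**Working it through.** **Step 1: put the four statements in one unit.** Table 7 gives an amount per intake and a frequency, so 50 mg × 2 = 100 mg per day.

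| Place | Starting daily dose | Target daily dose | Does 200 → 100 count? |
|---|---|---|---|
| Abstract, Variables | not stated | 100 mg | yes |
| Section 9.3.6 | not stated | 50 mg | no |
| Section 9.7.5 | 200 mg | 100 mg | yes |
| Table 7 (label text) | not stated | 2 × 50 = 100 mg | not a scoring rule |

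The targets differ by 100 ÷ 50 = 2. Read literally, no single change satisfies both 9.3.6 and 9.7.5: 200 → 100 counts only under 9.7.5, while 200 → 50 and 100 → 50 count only under 9.3.6. The exposure window also varies, being current use in the Abstract and continuous use in 9.3.6 and 9.7.5.

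**Step 2: is this only a trace of the amendment history?** No. The conflict lies between current sections. For Version 2.3, Table 1 records a dose-reduction correction in the Abstract and in 9.7.5, and no Version 2.3 entry names 9.3.6. The log also says that DUS1 analyses are unaffected, but not which definition they used.

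**Step 3: what the derived dose can show.** Daily dose = strength × quantity ÷ days of supply. Pack size is not in the protocol, so 56 tablets is an assumption.

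- 100 mg tablets, 28 days: 100 × 56 ÷ 28 = 200 mg per day
- 100 mg tablets, 35 days: 100 × 56 ÷ 35 = 160
- 100 mg tablets, 56 days: 100 × 56 ÷ 56 = 100
- 100 mg tablets, 60 days: 100 × 56 ÷ 60 = 93
- 50 mg tablets, 28 days: 50 × 56 ÷ 28 = 100

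Whatever the pack size, doubling the interval halves the derived dose. A pack of n tablets taken twice daily lasts n ÷ 2 days, so the doubled interval is n days. That stays within the 60-day limit for consecutive prescriptions if n ≤ 60, and within the 90-day sensitivity limit if n ≤ 90. For a larger pack, say 98 tablets, the derived dose at 60 days would be 100 × 98 ÷ 60 = 163 mg per day: distorted, but not halved.

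The effect depends on how the interval estimate is applied, which Section 9.3.1 leaves open.

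- Each patient's own interval: a late refill can look like a reduction.
- One common interval per pack: a late refill has no effect, but a real change in tablets per day is missed.

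Under both, a switch between 100 mg and 50 mg tablets is visible through the strength.

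**Step 4: how many users this touches.** The inputs are the preliminary counts in Table 10 (SIDIAP 3,375; THIN 1,640; GePaRD 4,867 to 9,735; Sweden 1,800 to 2,200; IACS pending) and the figure of about 4,000 GePaRD users in Section 9.4.2.

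- Table 10 low: total 3,375 + 1,640 + 4,867 + 1,800 = 11,682. GePaRD plus Sweden is 6,667 ÷ 11,682 = 57%; GePaRD alone is 42%.
- Table 10 high: total 3,375 + 1,640 + 9,735 + 2,200 = 16,950. GePaRD plus Sweden is 11,935 ÷ 16,950 = 70%; GePaRD alone is 57%.
- GePaRD 4,000, Sweden low: 5,800 ÷ 10,815 = 54%; GePaRD alone is 37%.
- GePaRD 4,000, Sweden high: 6,200 ÷ 11,215 = 55%; GePaRD alone is 36%.

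These are DUS1 counts. The protocol gives none for DUS2.

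**The case against.** The best defence is that Section 9.7.5 is the operative analysis text. It states a start and an end dose, names its output tables, and agrees with the Abstract and with the daily total of the Table 7 wording. A careful programmer would probably notice that 9.3.6 is out of line. This lowers the chance of harm but leaves the contradiction, because 9.3.6 is the section that defines the variable.

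On the derived dose, Section 9.9 already admits that days of supply often have to be estimated and that exposure may be misclassified. That stands in part. The section does not mention dose, and the planned sensitivity analysis varies the permitted gap between prescriptions (60 or 90 days), not the days of supply that drive the dose. The Abstract lists three risk-minimisation components that the study cannot fully address, and dose is not among them.

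A reader might go further in three ways that the protocol does not support.

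- *Daily dose cannot be observed in three of the five databases.* The plan estimates it with error from strength, quantity and days of supply. Only GePaRD is said outright to lack dose, and Section 9.4.2 lists dosage for Sweden.
- *Patients already below 200 mg per day dilute the percentage in Tables 18A and 18B.* Section 9.7.5 fixes no denominator, its wording can be read as restricting to patients at 200 mg, and the table shells are in files not shown.
- *Daily dose should be analysed only in SIDIAP and THIN.* DUS1 was already complete in four databases by January 2015, so this would break the comparison with DUS2.

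**Conclusion.** The contradiction is established from current text and needs no assumption: the daily-dose target is 50 mg in one section and 100 mg in two others, and the label wording in Table 7 totals 100 mg per day. It must be reconciled before the measure is programmed for DUS2. The protocol does not show that the whole posology result is invalid. Measured uptake near zero would arise only if a centre applied 9.3.6 literally and ignored both 9.7.5 and the Abstract.

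The derived-dose point is a secondary limitation. It applies where no prescribed dose is recorded and days of supply are estimated from intervals: GePaRD and IACS, with Sweden uncertain because Table 9 and Section 9.4.2 disagree. The user shares rest on preliminary counts without IACS. The milligram illustration rests on an assumed pack size and, for spurious reductions, on the use of patient-level intervals. Dosage patterns are a secondary objective, which also limits the weight of this part.

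**What to change.** 1. Reconcile Section 9.3.6, the Abstract, Section 9.7.5 and Table 7 to one dose-reduction definition, expressed as a daily dose with its start and end values and a single exposure window. Apply it in all databases and in both DUS1 and DUS2, and record which definition the completed DUS1 analyses used. The sponsor must settle which figure applies. This is a wording change; cost arises only if a completed DUS1 run proves to have used a different definition.

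2. Resolve whether a usable dosage field exists in the Swedish data, so that Table 9 and Section 9.4.2 agree.

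3. For databases without a recorded prescribed dose, keep the planned daily-dose analysis, report change of tablet strength alongside it, and say in Section 9.9 that a change in tablets per day cannot be separated from refill timing when days of supply are estimated. The cost is one extra tabulation, and comparability with DUS1 is preserved.
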